## **13 DATA HANDLING AND SOURCE DOCUMENTS**

Patient data will be collected on eCRFs and will be substantiated by source documents at the clinical site. The eCRFs will be completed according to guidelines provided by the Sponsor. Source documentation supporting the eCRF data should indicate the patient's participation in the study and should document the dates and details of all study procedures, AEs and patient status.

The Investigator must maintain source documents, such as laboratory reports, complete medical history, ECG read outs and physical examination reports. All source documents should be accessible for verification by the site monitor, auditor, the IRB, or for inspections by the regulatory authorities. In addition, the site will allow the Sponsor direct access to all source documents and will permit trial-related auditing of clinical, pharmacy and laboratory facilities.

Direct access to these documents must be guaranteed by the Investigator or their designee, or the study coordinator, who must provide support at all times for these activities.

The nature and location of all sources of original data required to complete the eCRF will be identified by the monitor and the site staff.

The Study Monitor will perform 100% source data verification to ensure adequate Quality Control (QC) and assurance of patient data. An explanation of missing data must be given.

All data entered into the eCRF will be saved directly into the study database. This data will be validated both manually and programmatically. Clarification of data will be requested from the

Page 66 of 84 AKARI Confidential study site as requested. The database will be quality assured and will be available for statistical analysis according to the SAP.

Patient data will be reviewed for major Protocol deviations by the Monitor during site visits and the entire team will review the database at timed intervals prior to the database lock.

All correspondence (e.g. with the Sponsor, or designee, IRB) relating to this study should be kept in the appropriate files. Records of patient's source documents, eCRF's, IMP inventory pertaining to the study must be kept on file.

If the Investigator moves, withdraws from the study or retires, the responsibility for maintaining the records may be transferred to another person who will accept responsibility. Notice of transfer must be made to and agreed by the Sponsor.

Biological samples may only be stored indefinitely for the purpose of additional research related to this protocol if the patient has given informed consent for additional scientific research (directly related to this protocol). If no informed consent was obtained, samples must be destroyed after the patient has completed all protocol treatment and procedures.

If the patient withdraws consent to participate in this study they may require all previously retained identifiable samples to be destroyed to prevent further analysis.

The patient will be informed about any unforeseen new analyses on retained identifiable material that were not foreseen when the patient consented to participate in the study and a new consent will be requested of the patient. The patient can refuse any new analyses and it will not influence their participation in the study.

Storage of biological samples on site is subject to the site's guidelines. When samples are shipped to another facility (e.g. a central laboratory), they should be stripped from any identifying information and labeled with a code (trial name, patient study number, date and time of collection).

# 14 QUALITY CONTROL AND QUALITY ASSURANCE

The hospitals/departments taking part in the trial are responsible for maintaining their own SOPs and Quality Assurance (QA) / QC procedures. The Sponsor or their delegate will also implement and maintain QC and QA procedures with written standard operating procedures (SOPs) to ensure that the study is conducted and data are generated, documented and reported in compliance with the Protocol and ICH GCP and all applicable regulatory requirements. The Sponsor or delegate will be responsible for monitoring the trial and carrying out 100% source data verification.

The study will be in accordance with the provisions of the Declaration of Helsinki and all revisions thereof, in accordance with ICH GCP and as required by applicable regulatory requirements.

Any necessary training for the study will be provided to Investigators and study personnel by the Sponsor or their designee prior to study initiation.

## 14.1 Ethical Conduct of the Study

The study will be conducted in accordance with all appropriate regulatory requirements and under an approved Protocol. The study will be conducted in accordance with current ICH GCP, all appropriate patient privacy requirements and the ethical principles outlined in the Declaration of Helsinki.

## 14.2 Ethical Considerations and EC or IRB Approval

The EC or IRB will safeguard the rights, safety and well-being of patients in the study by reviewing the following documentation; Protocol, ICF, any other written information given to patients, Investigator Brochure, safety updates, annual progress reports (if applicable) and patient recruitment procedures (if applicable) and any significant revisions to these documents.

The EC or IRB will be appropriately constituted in accordance with ICH GCP and local requirements as applicable. The study will commence only after the EC or IRB has given full approval and the Investigator has written approval. Additionally, the clinical trial may not commence until appropriate regulatory agreement has been obtained.

Amendments to the Protocol will be subject to the same requirements as the initial review. The Investigator will submit periodic reports and updates to the EC, as required and will inform the EC or IRB of any reportable AEs.

## **15 FINANCING, INDEMNITY AND INSURANCE**

The Sponsor will have a contract in place with the hospitals/universities and will be responsible for any payments to patients for payment of travel and other expenses reimbursable by the Sponsor on delivery of receipts.

The Sponsor has a clinical trials insurance policy in place, underwritten by AON Limited. A copy of the policy/certificate of insurance will be supplied separately.

AKARI Therapeutics Plc will indemnify the Investigators from all or any claims arising out of this study except for their negligence or malpractice and providing that the study is conducted according to the standards established by the Protocol.

## **16 PUBLICATION POLICY**

The key design elements of this Protocol will be posted in a publicly accessible database.

The CRO has no independent publication rights.

Akari Therapeutics Plc actively encourages publication of clinical trial data in reputable peer reviewed journals. Authorship will be discussed and agreed in advance. If the Investigator drafts a publication, he/she agrees to send it to Akari Therapeutics for review and comment before its submission to the journal. In cases where Akari Therapeutics considers that the proposed publication contains information which should be protected as valuable confidential information or is out of compliance with applicable laws and regulations, Akari Therapeutics reserves the right to delay submission to the journal, until the required deletion of the confidential information from the proposed publication has been removed.

# **17 STUDY RECORD RETENTION**

The Investigators shall ensure that the documents contained in the Investigator Site File are retained for 25 years after the conclusion of the trial. The Sponsor shall ensure that the documents contained in the Trial Master File are retained for 25 years after the conclusion of the trial. The Sponsor and Investigators will ensure that during this period the files are complete, legible and readily available to the licensing authority on request.

All data derived from the study will remain the property of Akari Therapeutics Plc.

All correspondence (e.g. with the Sponsor, or designee, EC or IRB relating to this study should be kept in the appropriate files. Records of patient's source documents, eCRF's, IMP inventory pertaining to the study must be kept on file.

If the Investigator moves, withdraws from the study or retires, the responsibility for maintaining the records may be transferred to another person who will accept responsibility. Notice of transfer must be made to and agreed by the Sponsor.

## **18 CLINICAL STUDY REPORT**

The results of this clinical study must be summarized by the Sponsor (or designee) and a final audited report must be retained on file. This report will include discussions on the study objectives, methodology, findings and conclusions. The PI(s) will be asked to review and comment on the draft report and the Chief Investigator will be required to sign the final version. All Investigators will be provided with a final copy of the Clinical study report. The report must be archived with all other study documents.

## **19 HANDLING OF BLOOD COLLECTION SAMPLES**

Samples should be handled according to the instructions provided in the Laboratory Manual.

## **21 APPENDIX**

## **21.1** Appendix 1 Laboratory Assessments Clinical Efficacy Assessments

The primary efficacy endpoint will be obtained from the clinical laboratory test panel for LDH values prior to Coversin administration on Study Days 1 (baseline), 43, 60, 90, 120, 150 and 180.

Secondary endpoints will be evaluated at these time points (above), as well as Day 28, to support development of the Coversin efficacy profile.

In addition, LDH will also be measured at Days 3, 7, 14, 21 and 36.

#### **Clinical Safety Assessments**

This is a mandatory minimum number of visits and procedures. Investigators may choose to see patients more frequently if appropriate and extra samples may be taken if needed.

#### **Quality of Life Questionnaires**

The patient will complete the EQ-5D-5L and FACIT at Day 1 (pre-dose, baseline), 7, 14, 21, 29, 36, 43, 60, 90, 120, 150 and 180. The data will be transcribed to the eCRF and subsequently analysed as a secondary efficacy endpoint.

The patient will complete a non-validated questionnaire at Day 29, 90 and 180 to determine whether self-injection by patients with PNH is well-accepted and the support provided sufficient.

#### Medical History and Present Conditions

A complete medical history will include evaluation (past and present) of the following:

- General
- Heart/cardiovascular
- Chest/respiratory
- Dermatological/skin
- Psychiatric assessment
- Past surgeries
- Substance abuse
- Hematologic/lymphatic
- Urogenital
- Endocrine/metabolic
- Allergies/drug sensitivities

#### **Physical Examination**

- General appearance
- Dermatological/skin
- Hematologic/lymphatic
- Heart/cardiovascular
- Respiratory
• Vein and injection site inspection

# Weight & Height

Patients' weights will be recorded at screening, baseline, Day 29 and Day 180. Height will be collected at baseline.

## Vital Signs

Blood pressure and pulse rate will be measured in the supine position after the patient has rested comfortably. Body temperature will be recorded using whatever device is routinely used in the Investigator's clinic (e.g. oral, ear etc.). Measurements will be recorded in the patient's eCRF.

# **Cardiac Safety**

Routine ECG should be performed at any time pre-dose within 7 days of the first dose, 1 hour after the first dose and at the conclusion of the study (Day 180). The ECG traces will be reviewed, signed, and dated by a physician and he/she will record on the trace whether the ECG is normal or abnormal and if deemed abnormal, whether the abnormality is clinically significant (CS) or not clinically significant (NCS).

### **Clinical Laboratory Safety Tests**

Additional and repeat testing may be performed at the discretion of the Investigator. All clinical laboratory safety tests will be performed locally by each clinical unit.

## Hematology Parameters (Local Laboratory Testing)

White blood cell count	Neutrophils absolute
Red blood cell count	Lymphocytes absolute
Hemoglobin	Monocytes absolute
Mean Cell Hemoglobin (MCH)	Mean Cell Hemoglobin Concentration (MCHC)
Hematocrit	Eosinophils absolute
Erythrocyte sedimentation rate (ESR)	Basophils absolute
Platelets	Mean Cell Volume (MCV)
Reticulocytes	

#### **Chemistry Parameters (Local Laboratory Testing)**

LDH Sodium Potassium Bicarbonate Urea Creatinine	Glucose (Random) Alkaline phosphatase Alanine Aminotransferase (ALT) Aspartate Aminotransferase (AST) Creatine Kinase (CK) Total Bilirubin
Chloride	Bilirubin (Direct) (only if Total is elevated)
Albumin Calcium Gamma Glutamyl Transpeptidase (GGT)	Phosphate (Inorganic) Protein (Total)

## Urinalysis Parameters (Local Laboratory Testing)

Leukocytes	Ketones
Protein	Nitrates
Bilirubin	Blood (absolute)
Glucose	hCG (female patients)
pH	Specific gravity

### At Discretion of PI Based on Urinalysis Results

Microbiology Urine Microscopy Pregnancy testing Urobilinogen

#### Fluorescent Aerolysin (FLAER)

Taken at baseline and Day 180.

#### **Pregnancy Test**

Pregnancy testing will be conducted at screening for female patients and monthly thereafter. Baseline and Day 180 will be serum samples. The monthly tests will be performed as a urine pregnancy test.

#### **Central Laboratory Testing**

LTB4 CH50 (PD) Total C5 Levels Anti-Drug Antibody (ADA) Unbound Coversin level (PK) LDH Isoenzymes

Table 11: AK585 Schedul of Events	e		60 mg fo	llowed by	30 mg 12	2hrs later		22.5 mg twice daily Initiation Phase											
Evaluation &	Screening	overnight stay							ny 2	Day 3	Day 7 (±3 days)		_	Day Inten ov	Day 21 (±3 days)				
Procedures	Up to -14 days	Baseline Pre- 60mg dose	3hrs Post 60mg dose	6hrs Post 60mg dose	9hrs Post 60mg dose	12hrs Pre 30mg dose a	18hrs Post 30mg dose b	24hrs Pre- 22.5mg dose	36hrs Pre- 22.5mg dose	48hrs Pre- 22.5mg dose	Pre- 22.5mg dose	Pre- 22.5mg dose	3hrs Post- 22.5mg dose	6hrs Post- 22.5mg dose	9hrs Post- 22.5mg dose	12hrs Pre- 22.5mg dose a	18hrs Post- 22.5mg dose b	24hrs Pre- 22.5mg dose	Pre- 22.5mg dose
Eligibility, ICF & Medical History and demographics	x																		
Physical Examination 	х										х	х							х
Nasal & Throat Swabs 	х																		
Vital Signs  (including height & weight)	х	х						x		х	х	х						х	х
ECG 		x	х																
CH50 (PD)		х	x	х	х	x	x	х	х	х	х	х	х	х	х	х	х	x	х
Coversin Drug Level (PK)		x	x	x	x	x	x	x	x	x	х	x	x	x	x	x	x	х	х
Total C5		x	х	х	х	х	х	х	х	х		х	х	х	х	х	х	х	х
Antibodies (ADA)		x									х	х							х
LTB4		х		х		x		х	х		х	х							х
LDH Isoenzymes		х																	
FLAER		х																	
Meningitis prophylaxis 									As per si	te schedule									
Chemistry including LDH	x	x								х	х	х							х
Hematology	х	х								х	х	х							х
Urinalysis		x				х		х		х	х	х							х
Pregnancy Test Monthly 	х	Serum																	
Questionnaire on Self Injection																			
EQ-5D-5L & FACIT		x									х	х							х
Drug Accountability											х	х							x
IMP administration (±1hr)		x				x		x	x	x	х	x				x		х	х
AEs & Concomitant Medications	х	x	х	х		х	х	х	х	х	х	х	х	х		х	х	х	х

Page 75 of 84 AKARI Confidential

Table 11: AK585 Schedule of Events	45 mg once daily Maintenance Phase														
Evaluation &	Day 29 (±3 days)			Inte	36-37 (± 3 ) nse Monito overnight sta	ring		Day 43 (±3 days)	Day 60 (±3 days)	Day 90 (±3 days)	Day 120 (±3 days)	Day 150 d (±3 days)	Day 180 (±3 days) Early Termination	Follow up Visit	
Procedures	Pre- 45mg dose	Pre- 45mg dose	3hrs Post- 45mg dose	6hrs Post- 45mg dose	9hrs Post- 45mg dose	12hrs Post- 45mg dose	18hrs Post- 45mg dose	24hrs Pre- 45mg dose c	Pre- 45mg dose	Pre- 45mg dose	Pre- 45mg dose	Pre- 45mg dose	Pre- 45mg dose	Pre- 45mg dose	Day 210 (+5 days) e
Eligibility, ICF & Medical History										X 7					
Physical Examination 1	х	х								х	х	x	х	х	х
Nasal & Throat Swabs 															
Vital Signs  (including height & weight)	x	х						х		х	х	х	х	х	х
ECG 											х	х	х	х	
CH50	х	х	х	х	х	х	х	х	х	х	х	х	х	х	х
Coversin Drug Level (PK)	х	х	х	х	х	х	х	х	х	х	х	х	х	х	х
Total C5	х	х	х	х	х	х	х	х		х	х	х	х	х	х
Antibodies (ADA)	x	х								х		x		х	х
LTB4	х	х							х	х		х		х	х
LDH Isoenzymes											х			х	
FLAER														х	
Meningitis prophylaxis 5								As per s	ite schedule	-					
Chemistry	x	х							х	х	х	x	х	х	х
Hematology	х	х							х	х	х	x	х	х	х
Urinalysis	x	х								х	х	x	x	х	х
Pregnancy Test Monthly 	х									х	х	x	х	Serum	х
Questionnaire on Self Injection	x										х			Х	
EQ-5D-5L & FACIT	х	х							х	х	х	х	х	Х	
Drug Accountability	х	х							х	х	х	х	х	Х	
IMP administration (±1hr)	х	х				х		х	х	х	х	х	х	Х	
AEs & Concomitant Medications	х	х	х	х		х	х	х	х	х	х	x	x	х	х

a These samples are to be taken 12hrs after the first dose in the morning and pre-second dose of Coversin

b These samples are to be taken 18hrs post dose referring to the first Coversin dose given the morning before

° This sample is to be taken 24hrs after the last Coversin dose and prior to the next 24-hourly dose

d Day 150 – Investigator and patient to confirm if patient will continue onto the long-term safety trial or begin alternative treatment. At Day 181, the patient will enter the long-term safety trial on Coversin or begin alternative treatment and not enter the long-term safety trial.

e Safety follow up visit is not required if the patient is entering the long-term safety and efficacy trial

-  Physical Examination Inclusive of vein assessment and injection site inspection.
- (2) Nasal & Throat swabs Any positive Neisseria sp. results will be grounds for excluding the patient from the trial, and will mandate special vigilance on the part the Investigator and all medical and nursing staff. Repeat throat and nasal swabs should then be taken at weekly intervals until the organism has been eradicated and prophylactic antibiotic cover should be maintained as per standard of care. The patient can then begin the trial.
- (3) Vitals Diastolic and Systolic blood pressure, pulse rate and oral temperature (weight only required at Screening, Baseline (pre-dose Day 1), Day 29 and Day 180 and height is only required at Baseline).
- (4) Routine ECG at any time pre-dose within 7 days of the first dose, 1 hour after the first dose and at the conclusion of the study at Day 180. ECG A pre-dose standard ECG can be done at any time within 7 days of the first dose and between 1 and 6 hours post-dose and at the end of the study.
-  This Protocol is flexible and permits each site to follow their own standard of care procedures for Meningitis prophylaxis. It is expected that the patient will receive at least 14 days of an appropriate antibiotic post first dose of Coversin and no vaccines are to be given during the change from 12 hourly dosing to 24 hourly dosing.
-  Serum Pregnancy test will be performed at Baseline and end of treatment Day 180 or early termination. Throughout treatment, monthly urine pregnancy tests will be performed.

(7)

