## Intensive Monitoring Clinic Day 36-37 (±3 day window)

If the patient is responding well to once daily dosing, an overnight stay is required at Day 36 to perform Intensive PK sampling at timepoints 3hrs, 6hrs, 9hrs, 12hrs, 18hrs & 24hrs. A 30-minute window to draw blood is permitted.

On Day 43 a clinic visit will take place and a local and central blood draw will be taken.

Central and local Blood draws will be taken at the clinic during the clinic visits on Day 60, 90, 120, 150 and 180 (±3 day window).

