## **5.3 Procedure for Increase in Frequency of Doses**

Evidence from animal PK/PD studies, single and multiple dose studies in normal volunteers and experience in 10 patients suggest that an inadequate response or breakthrough hemolysis is highly unlikely to occur during the AD or Initiation Phase.

On completion of the Initiation Phase, a single 45 mg daily maintenance dose will be given for the remainder of the trial unless, it becomes apparent that full complement inhibition is not being maintained, in which case appropriate dose interval adjustments will be made and the patient will revert back to 22.5 mg twice daily after receiving another AD.

The maintenance dose can be changed after Day 36 if there is evidence of CH50 > 10 CH50 U Eq/mL, a rise in serum LDH for two consecutive readings of over 0.4 x ULN or a single rise over 0.8 x ULN above the lowest level previously achieved or clinical symptoms. In this case the dose should revert back to 12-hourly dosing (assuming compliance is satisfactory and that the patient has not missed any doses) or consideration should be given to the patient withdrawing from the study.

The schedule for dosing during the Initiation and Maintenance Phases, is as follows:

	Inadequate	Response		
Exis	ting	Swit	tch to	
Dose	Interval	Dose	Interval	
22.5 mg	12 hourly	Withdraw patient		
45 mg	24 hourly	22.5 mg	12 hourly	

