## 11.2.3 Overdose

All overdoses with or without associated symptoms, should be reported as AEs on the appropriate eCRF page. An overdose is defined as dose exceeding the specified dose for each week. If sequelae meeting the criteria for a SAE have occurred in association with the overdose, the case must be reported immediately, within 24 hours. An assessment whether the overdose was accidental or intentional should be recorded. If the overdose was a suicide attempt, this fact should be clearly stated. The AEs and SAEs that occur as a result of an overdose should be recorded on the eCRF.

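### The Day 36-37 block of the Schedule of Events marks a dose at 12 h, which contradicts once-daily maintenance dosing

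*Combined protocol and SAP*

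**What the plan says.** Maintenance is once daily throughout the protocol. Table 8 (section 5.1) gives a morning dose of 45 mg from Day 29 and no evening dose. Section 5.3 says that "a single 45 mg daily maintenance dose will be given for the remainder of the trial", unless complement inhibition is not being maintained. The Day 36-37 stay is described in section 5.2: "If the patient is responding well to once daily dosing, an overnight stay is required at Day 36". The text then lists sampling times only and mentions no second dose.

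The maintenance page of Table 11 is headed "45 mg once daily Maintenance Phase", and its 12 h column for Day 36-37 is labelled "12hrs Post- 45mg dose". Footnote c says of the 24 h column: "This sample is to be taken 24hrs after the last Coversin dose and prior to the next 24-hourly dose". Yet the row "IMP administration (±1hr" is marked at pre-dose, 12 h and 24 h in that block. Table A-12 repeats the pattern. Neither table explains the 12 h mark or gives a dose for it.

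In the twice-daily Day 14-15 block of Table 11, the 12 h column is labelled "12hrs Pre- 22.5mg dose", and a dose there is correct.

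**The concern.** Section 5.2 sends sites to Table 11 for visit procedures and blood draws, and this row tells them when to give study drug. On Day 36 the patient stays overnight in a supervised setting, so a mark at 12 h could be acted on.

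Two things would follow if it were. First, the patient would receive a dose that Table 8 does not provide for. Section 11.2.3 states: "An overdose is defined as dose exceeding the specified dose for each week", and requires every overdose to be reported as an adverse event. In a trial of up to 6 patients whose primary objective is safety, a table error would be generating reportable events.

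Second, Day 36-37 is the only visit that samples CH50, drug level and total C5 serially under once-daily dosing. The 18 h and 24 h samples show whether 45 mg lasts the full interval. After a 12 h dose they would no longer describe once-daily dosing.

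**Working it through.** The plan gives no figure to reproduce. The check has three parts: where the mark sits, whether any reading makes it correct, and what following it would do.

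**1. Position of the mark.** The maintenance page of Table 11 has 15 data columns:
- column 1: Day 29
- column 2: Day 36 pre-dose
- columns 3 to 8: 3, 6, 9, 12, 18 and 24 h
- columns 9 to 14: Days 43, 60, 90, 120, 150 and 180
- column 15: Day 210

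The CH50 row is filled in all 15, which fixes the alignment. The dosing row also has 15 cells, with marks in columns 1, 2, 6, 8 and 9 to 14. Column 6 is 12 h. Neighbouring rows agree with this alignment: vital signs are marked at 24 h, and chemistry is blank from 3 h to 24 h. Table A-12 gives the same result, so a text-extraction fault is unlikely.

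**2. Comparison with the rest of the plan.**

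| Source | Dose at 12 h on Day 36? |
|---|---|
| Table 11 and Table A-12, dosing row | Yes, size not stated |
| Table 11 and Table A-12, page header | No, once daily |
| Table 8, section 5.1 | No evening dose after Day 28 |
| Section 5.2, Day 36-37 stay | Sampling only, once-daily responders |
| Section 5.3 | Single daily dose |
| Footnote c | No; the 24 h sample must be 24 h after the last dose |

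The marks at pre-dose, 12 h and 24 h match those of the Day 14-15 block. Carry-over from that block is the likely source.

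**3. Effect if the mark were followed.**

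Time since last dose:
- 18 h sample: 18 − 12 = 6 h instead of 18 h
- 24 h sample: 24 − 12 = 12 h instead of 24 h

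The serial profile has 7 points (pre-dose, 3, 6, 9, 12, 18 and 24 h), and 2 of the 7 are affected. With 6 patients, all sampled and all dosed at 12 h, that is at most 2 × 6 = 12 of 7 × 6 = 42 draws.

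Dose, taking the unstated size as either 22.5 mg or 45 mg (assumption):

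| | Planned | Extra 22.5 mg | Extra 45 mg |
|---|---|---|---|
| 0 to <24 h | 45 mg | 45 + 22.5 = 67.5 mg | 45 + 45 = 90 mg |
| Week | 7 × 45 = 315 mg | 315 + 22.5 = 337.5 mg | 315 + 45 = 360 mg |
| Weekly excess | – | 22.5/315 = 7.1% | 45/315 = 14.3% |

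At nominal dosing times, the 90 mg case equals but does not exceed the Day 1 ablating total (60 + 30 mg) and the 24-hour limit in section 5.4.

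**Not directly affected:**
- the 3, 6 and 9 h samples, and the 12 h sample if drawn before the dose
- seven once-daily CH50 and drug-level troughs: Day 36 pre-dose and Days 43, 60, 90, 120, 150 and 180
- the LDH values for the primary endpoint, which come from Day 1 and Days 43 to 180

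**The case against.** The best case on the other side is that this is a stray mark that the plan overrules many times. The page header, column label, footnote c, Table 8 and sections 5.2 and 5.3 all point to once-daily dosing. With no dose given, a site would have to invent one. Nothing in the documents shows that any site did. This stands, and it limits the weight of the point.

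The analytic loss is also small. The serial profile is not an endpoint in section 3.2, and section 12.1 plans no analysis of it. The figure of 12 draws needs full enrolment and the same error for every patient. This stands too.

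The overdose argument can be questioned because the protocol tabulates no weekly dose, and a dose marked in the schedule might be called specified. That is weaker. Seven daily doses of 45 mg is the plain reading of the regimen, and the mark specifies no amount.

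The mark might be meant for patients already returned to 12-hourly dosing. Section 5.3 allows a change only after Day 36, but that does not fully exclude it, because section 6.2 requires immediate reversion for a thrombotic event after Day 29. What makes the reading untenable is that section 5.2 limits the stay to once-daily responders and every column in the block is labelled 45 mg.

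Finally, the diary card records injection times, so samples after an extra dose could still be used in the sponsor's PK/PD model. That is true, but they would not belong in a once-daily profile.

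**Conclusion.** The concern holds. The 12 h dosing mark in the Day 36-37 block is wrong in both tables and should be corrected. It is a clerical error, but it sits in a dosing instruction.

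The harm is conditional on a site following the mark. In that case the patient's weekly dose would exceed plan by 7.1% or 14.3%, depending on an assumed extra dose of 22.5 mg or 45 mg, and either would be a reportable overdose on the plain reading of section 11.2.3. Two of the seven serial samples would be lost to the once-daily profile. The primary endpoint and the seven CH50 and drug-level troughs would not be directly affected.

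**What to change.** Delete the 12 h dosing mark from the Day 36-37 block in Table 11 and in Table A-12, and send sites a short notice that no dose is due at 12 h. Doses then fall at 0 h and 24 h only, and the 18 h and 24 h samples are 18 h and 24 h after the last dose, as the column labels and footnote c require.

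For any patient already sampled, record whether a 12 h dose was given. If it was, leave the 18 h and 24 h samples out of the once-daily profile and record the extra dose under section 11.2.3.

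As a separate minor correction that adds no weight to this point, the Appendix 2 regimen table should place the Day 1 30 mg dose in the evening window (7pm to 11pm), to agree with its own text and Table 8.

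The cost is two table cells and one regimen line in the next amendment, plus the notice. No visits or samples are added.
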